7. RATIONALE AND BACKGROUND

Asthma is a respiratory condition that causes symptoms of wheezing, shortness of breath, chest tightness and cough [[P18-03927](#)]. According to treatment guidelines, asthma patients at treatment step 3 and above should be treated with inhaled corticosteroids often in combination with long-acting beta agonists. However, many patients continue to have symptoms despite the use of these agents [[P10-08936](#)].

In late 2014, Spiriva Respimat (tiotropium), a long acting anticholinergic, was approved for treatment of asthma in the UK. Since this time, it has been approved for use in asthma patients in other countries including Japan and the United States. In the U.K., Spiriva® Respimat® is indicated as an add-on maintenance bronchodilator treatment in adult patients with asthma who are currently treated with the maintenance combination of inhaled corticosteroids ($\geq 800\mu\text{g}$ budesonide/day or equivalent) and long-acting beta2-agonists and who experienced one or more severe exacerbations in the previous year.

The current BTS/SIGN Guideline for the management of asthma recommends tiotropium by soft-mist inhaler as an alternate controller therapy at steps three, four and five of the asthma treatment paradigm, on top of inhaled corticosteroid (ICS)/LABA [[P18-03927](#)]. Alternatively, these patients could also be treated with a higher dose of ICS or ICS/LABA or MART, addition of leukotriene receptor antagonist (LTRA), addition of theophylline, beta agonist tablet, or switching to a different ICS/LABA, as shown in [figure 1](#).

Protocol for non-interventional studies based on existing data

BI Study Number 0205-0537

c25002535-01

Proprietary confidential information © 2018 Boehringer Ingelheim International GmbH or one or more of its affiliated companies

[figure not shown]

Figure 1 Summary of asthma management in adults.

Tiotropium is the first of its class approved for the use in the treatment of asthma. After a drug is launched in the market, it is important to identify patient clinical and socio-demographic characteristics of patients who initiate this treatment as opposed to other available treatments for patients at the same stage of disease. This type of study will allow us to evaluate potential channeling of prescribing to different patient populations. The results of the current study can also be used to determine the variables included in the calculation of propensity scores in future studies.

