9.3.3 Covariates

The following patient characteristics will be assessed in this study:

Demographic characteristics:

- Age on the index date (continuous variable in years)
- Age on the index date (categorical variable: 18-34 years, 35-49 years, 50-64 years, 65 years and above)
- Gender (male, female)
- Ethnicity (if available)
- Patient level Index of Multiple Deprivation (IMD)

Lifestyle factors

- Smoking status (closest to index date; if available)
- Alcohol consumption (closest to index date; if available)
- Body mass index (BMI) (closest to index date; if available)
- Systolic and Diastolic Blood pressure measurement (closest to index date; if available)

Asthma history and lab tests

- Number of asthma exacerbations in the year prior to the index date. This is defined as as ≤ 300 mg oral corticosteroids (OCS) (not prescribed during an annual asthma review), or an Accident and Emergency (A&E) visit, or hospital admission. Exacerbations recorded within 14 days after the index 1 were considered part of the same exacerbation.
- Royal College of Physicians (RCP) 3 Questions for Asthma score on the index date, or when it was not recorded on the index date, during the pre-index period (the one closest to the index date) (each question scored 0 (no) or 1 (yes) for the following three questions: “Have you had difficulty sleeping because of your asthma symptoms (including cough)?” “Have you had your usual asthma symptoms during the day (cough, wheeze, chest tightness or breathlessness)?” and “Has your asthma interfered with your usual activities (e.g., housework, work, school, etc)?” [R18-1720]).
- Number of all-cause hospitalization in the year prior to the index date
- Number of respiratory disease related hospitalization in the year prior to the index date

Protocol for non-interventional studies based on existing data

BI Study Number 0205-0537

c25002535-01

Proprietary confidential information © 2018 Boehringer Ingelheim International GmbH or one or more of its affiliated companies

- Eosinophil count on the index date, or when it was not recorded on the index date, during the pre-index period (the one closest to the index date) (if available)

Comorbidities

- Respiratory
 - Pneumonia
 - Bronchiectasis
- Cardiovascular
 - Ischaemic heart disease
 - Myocardial infarction (MI)
 - Angina pectoris
 - Aneurysm
 - Hypertension,
- Renal failure
- Diabetes mellitus (any type)
- Psychiatric disorders
 - Dementia
 - Delerium
 - Depression
- Stroke

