- Allergic rhinitis
- Sinusitis
- Charlson comorbidity index [[R08-1584](#)]
- Cataract
- Osteoporosis
- Obesity

Concomitant prescriptions

- Asthma-related prescriptions in the year prior to index date
 - Short-acting beta agonists
 - Inhaled long-acting beta agonists (on top of ICS/LABA FDC)
 - Inhaled corticosteroid (ICS) (on top of ICS/LABA FDC)
 - Oral corticosteroid
 - Theophylline
 - Leukotriene Receptor Antagonist (LTRA)
 - Azithromycin,
 - Mucolytics
- Cardiovascular medications
 - Cardiac Glycosides
 - Thiazides
 - Loop diuretics
 - Antiarrhythmics
 - Beta blocker
 - Vasodilator Antihypertensive Drug
 - Centrally Acting Antihypertensive Drugs
 - Alpha-adrenoceptor Blocking Drugs
 - Drugs affecting the renin-angiotensin system

- Angiotensin Converting Enzyme Inhibitors
- Angiotensin II receptor blockers
- Renin Inhibitors
- Other antihypertensives
- Nitrates
- Calcium channel blockers
- Oral anticoagulants
- Heparin and other low molecular weight heparins
- Aspirin
- Antiplatelet
- Lipid-regulating Drugs
 - Bile Acid Sequestrants (lipid-regulating Drugs) - including Colesevelam
 - Ezetimibe (only in combination with Statin)
 - Fibrates
 - Statins
 - Nicotinic Acid Group
 - Omega-3 Fatty Acid Compounds
 - Other lipid-regulating drugs
- Glucose-lowering agents
- Non-steroidal anti-inflammatory drugs
- Psycholeptics
- Antipsychotics
- Antidepressants
- Agents for dementia

For concomitant medications used for diseases other than asthma the look-back time period will be limited to 180 days prior to the index date to increase the likelihood that the medications were used concomitantly. Concomitant medications will be categorized as current use (up to and including 60 days before index date) and past use (use any time prior to the 60 days before index date).

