9.4 DATA SOURCES

In the UK, nearly all residents are registered in a general medical practice that uses electronic medical records. Some of those records are available for research purposes in the CPRD. CPRD contains diagnostic and prescribing information recorded by general practitioners (GPs) as part of their routine clinical practice in the UK. The database currently contains data for over 13.2 million patients with research-quality data from 680 UK practices; 5.69 million of these patients are active (still registered with a contributing GP practice) [[R14-5257](#)]. Patients registered are representative of the whole UK population in terms of age and sex.

Data collection happens as part of normal clinical care of patients in participating practices on a daily basis. Patients are included in the primary care dataset from their first until their last contact with the participating practice. Data are collected by practices and usually uploaded to the CPRD secure servers on a monthly basis.

Protocol for non-interventional studies based on existing data**BI Study Number 0205-0537****c25002535-01**

Proprietary confidential information © 2018 Boehringer Ingelheim International GmbH or one or more of its affiliated companies

The CPRD contains data on demographic information, prescription details, clinical events (symptoms, diagnoses), preventive care provided, tests, immunisations, specialist referrals, hospital admissions and their major outcomes, and details relating to death. It should be noted that the CPRD only has prescription data but not the actual dispensing data. Data are largely recorded by general practice staff using version 2 Read codes, a hierarchical clinical classification system containing over 96, 000 codes. Numerical data on additional clinical measures (e.g. height, weight, blood pressure, alcohol intake) can also be recorded during consultations. Prescriptions issued by the GP are automatically recorded with a product name and British National Formulary code, alongside the dosage instructions and quantity. Results of laboratory tests ordered by the GP are commonly added to the patient record via electronic links to laboratories. Data fed back to the GP from other sources may also be entered into the patient record by practice staff; this might include information from secondary care such as key diagnoses, discharge data from hospitals, or follow-up information from specialist clinics. [[R16-1231](#)]

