In addition, the following CPRD-linked data will be used in this study:

- Hospital Episode Statistics (HES) Admitted Patient Care (HES APC) data
- HES Accident and Emergency (HES A&E) data
- Patient Level Index of Multiple Deprivation

HES APC data are collected on all admissions to National Health Service (NHS) hospitals in England. HES APC also covers admissions to independent sector providers (private or charitable hospitals) paid for by the NHS. HES APC does not cover accident and emergency (A&E, emergency department) attendances or outpatient bookings. In the financial year 2014/15 (April to March), 18,731,987 hospital episodes from 451 different NHS hospital trusts (known as ‘providers’) were recorded in HES APC. HES APC provides detailed clinical, demographic and organizational information for each Finished Consultant Episode. Data on drugs prescribed through hospital pharmacies to inpatients are not available in HES APC [[R18-0523](#)]. In this study, HES APC will be used to assess hospitalization (all-cause, respiratory disease related, or asthma or lower respiratory condition related) in the year prior to the index date among patients who were treated at English NHS health care providers. HES A&E data consist of individual records of patient care administered in the accident and emergency setting in England. These data are a subset of national A&E data collected by NHS England to monitor the national standard that 95% of patients attending A&E should wait no longer than 4 hours from arrival to admission, transfer or discharge. A&E data are submitted by A&E providers of all types in England. Data collected includes details about patients’ attendance, outcomes of attendance, waiting times, referral source, A&E diagnosis, A&E treatment (drugs prescribed not recorded), A&E investigations and Health Resource Group [[R18-0524](#)]. In this study, HES A&E will be used to ascertain A&E attendance for asthma or low respiratory conditions, which will be used to calculate the number of asthma exacerbation in the year prior to the index date.

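### The exacerbation count accepts oral steroids of at most 300 mg without saying per day, prescription or course, so under some readings low-dose repeat supply counts as exacerbations

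*Protocol*

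**What the plan says.** Protocol section 9.3.3, under asthma history, defines the number of exacerbations in the year before the index date through three alternatives. The first is oral corticosteroids: "This is defined as as ≤ 300 mg oral corticosteroids (OCS) (not prescribed during an annual asthma review". The others are "or an Accident and Emergency (A&E) visit, or hospital admission". A merging rule follows: "Exacerbations recorded within 14 days after the index 1 were considered part of the same exacerbation".

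The same section has a separate oral corticosteroid row under "Asthma-related prescriptions in the year prior to index date". It does not split acute courses from repeat supply.

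Section 9.4 says that GP prescriptions are recorded "alongside the dosage instructions and quantity". On the emergency-department linkage it states the purpose as follows: "ascertain A&E attendance for asthma or low respiratory conditions, which will be used to calculate the number of asthma exacerbation". For admissions it says "HES APC will be used to assess hospitalization (all-cause, respiratory disease related, or asthma or lower respiratory condition related", without stating which of these categories feeds the exacerbation count.

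Section 7 gives a UK indication limited to patients "who experienced one or more severe exacerbations in the previous year". Section 9.7.1 treats an absolute standardised difference (ASD) of at least 10% as meaningful.

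**The concern.** The steroid criterion is an upper limit with no lower limit and no unit. The text requires no asthma or exacerbation code alongside the prescription. It removes nothing for repeat or maintenance use except what was issued at the annual review. An analyst who follows the protocol, as section 9.8 requires, must choose a reading, and the readings give different counts for the same patient.

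The row matters because the study is meant to show whether Spiriva Respimat is channeled to particular patients, and the indication refers to severe exacerbations in the previous year. Section 7 adds that the results may guide the choice of propensity-score variables in later studies. A count that mixes ongoing steroid supply with exacerbations, or that drops larger acute courses, could make groups look different, or alike, for the wrong reason.

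**Working it through.** The plan gives no figure that depends on this definition, so there is none to reproduce. The check applies the rule as written. From section 9.3.3: ceiling 300 mg, merge window 14 days, counting window one year (365 days). From section 9.7.1: ASD threshold 10%. Doses and supply intervals below are arithmetic illustrations, not figures from the documents.

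**1. What the ceiling admits per prescription.** Highest daily dose that passes = 300 / days supplied.
- 28 days: 300/28 = 10.7 mg/day. 56 days: 300/56 = 5.4 mg/day.
- Repeat-type supplies that count: 5 × 28 = 140 mg; 10 × 28 = 280 mg; 5 × 56 = 280 mg. Not counted: 15 × 28 = 420 mg; 10 × 56 = 560 mg.
- Short courses that count: 40 × 7 = 280 mg; 30 × 10 = 300 mg. Not counted: 50 × 7 = 350 mg; 30 × 14 = 420 mg.

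So the ceiling filters larger repeat supplies, admits low-dose ones and drops some acute courses.

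**2. Whether the 14-day merge removes repeats.** Events in 365 days, over every possible start day:

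| Interval between repeats | 365 / interval | Counted events |
|---|---|---|
| 28 days | 13.04 | 13–14 |
| 30 days | 12.17 | 12–13 |
| 56 days | 6.52 | 6–7 |

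Each interval exceeds 14 days, so nothing is merged, whether the window runs from the first record or is chained from record to record.

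**3. The readings side by side.**

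| Basis of 300 mg | Low-dose repeats | Acute course above 300 mg |
|---|---|---|
| Per day | counted separately | counted, unless its daily dose exceeds 300 mg |
| Per prescription | counted separately | missed if on one prescription, unless A&E or admission |
| Per course, each prescription its own course | counted separately | missed, unless A&E or admission |
| Per course, continuous supply joined | mostly excluded | missed, unless A&E or admission |

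For the last row: 5 mg × 61 days = 305 mg, above the ceiling. Over a full year of continuous supply, any dose above 300/365 = 0.82 mg/day exceeds it.

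**4. Possible effect on the ASD (illustration only).** Every input here is assumed. True rates are equal in both groups, with mean m = 0.6 a year and negative binomial dispersion k = 0.5. R is repeats per year, p the share on repeat supply, and h the share of those at or below 300 mg per repeat.

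Mean = m + R·p·h. Variance = m + m²/k + R²·p·h·(1 − p·h). ASD = difference in means / √(average variance).

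Worked case, R = 13, h = 1, p = 2% against 0.5%: difference = 13 × 0.015 = 0.195. Base variance = 0.6 + 0.36/0.5 = 1.32. Group variances = 1.32 + 169 × 0.02 × 0.98 = 4.632 and 1.32 + 169 × 0.005 × 0.995 = 2.161, average 3.397. ASD = 0.195/1.843 = 0.106.

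| Repeat use | R=13, h=1 | R=7, h=1 | R=13, h=0.5 | R=7, h=0.5 |
|---|---|---|---|---|
| 2% vs 0.5% | 0.106 | 0.076 | 0.063 | 0.041 |
| 10% vs 2% | 0.320 | 0.280 | 0.209 | 0.170 |

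A second illustration (Poisson counts, true means 0.5 to 1.5, 12 false events per repeat user, shares from 2% vs 1% to 10% vs 3%) gives about 0.06 to 0.28. Both sets lie on either side of 0.10. Neither models missed acute courses, which pull the count the other way.

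**5. A&E visits and admissions.** Section 9.3.3 names no cause for either. Section 9.4 limits the A&E attendances used in this count to asthma and lower respiratory conditions. For admissions it lists three categories. All-cause and respiratory admissions have their own rows in 9.3.3; the third matches no other row, so the exacerbation count is its evident use, but no sentence says so.

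**The case against.** The strongest reply is that an upper limit makes sense as a filter for short courses. If 300 mg is a course total and continuous supply is one course, a long repeat series exceeds the ceiling and drops out. That is a possible reading, so a reader who infers that low-dose repeats are bound to be counted goes further than the text allows. But no sentence joins repeats into a course, just as none separates them. Nor do the documents show that the direction of the inequality is a mistake, or that 300 mg is the wrong figure; the absent rationale is only an omission.

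A reader might also infer that the comparison will cross the 10% threshold. The documents do not support that: they give no share of repeat users. Three of the four cells in the smaller scenario stay below 0.10, and the larger one assumes a five-fold imbalance. Section 9.7.1 also reports medians, IQR and maxima. Under the illustrative model the quartiles stay at 0, 0 and 1 even with 10% repeat users, and a maximum of 13 or more would signal the artefact. The oral-steroid and hospitalisation rows show part of any imbalance too. These points limit the harm. They do not give the row a single meaning.

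It could be said that such detail belongs in a statistical analysis plan. A programming algorithm may, but the protocol itself fixes this criterion and leaves its count dependent on an unstated basis. Finally, a reader might infer from 9.3.3 that A&E visits for any cause count; section 9.4 already rules that out.

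**Conclusion.** The point holds in limited form. The steroid criterion has no stated basis of measurement and excludes only annual-review prescriptions. On a per-day or per-prescription reading, low-dose repeats count separately: 13 to 14 events a year at 28-day intervals, which follows from the rule and the interval alone. On a per-prescription or per-course reading, acute courses above 300 mg are lost unless an A&E visit or admission accompanied them. On one course-based reading the ceiling removes most repeat series, but the text does not adopt it.

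The size and direction of the effect on the ASD cannot be determined from the documents; the ASD figures above rest wholly on assumed inputs. One covariate in a descriptive study is affected, and no eligibility criterion, named outcome or study size depends on it. It is still worth correcting before analysis, given its link to the indication and to channeling. The A&E and admission mismatch is a smaller matter of alignment.

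**What to change.** In section 9.3.3:

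(a) State whether 300 mg applies per day, per prescription or per course, and have the sponsor confirm the direction of the inequality. No threshold is proposed here. Exclude from the count oral steroid supply identified as continuous or maintenance from the recorded dosage instructions, quantity and interval: prescriptions whose days of supply run on from one another, not short courses that merely recur. Report the share of such users in each treatment group.

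(b) Carry the A&E restriction of section 9.4 into the definition, and tie the asthma or lower respiratory admission category to the count explicitly, so that admissions for other causes are not counted as asthma exacerbations.

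The cost is the rewording of one definition and modest programming on fields already held. The downside is some misclassification where dosage instructions are unclear, and the possible loss of some genuine frequent exacerbators.

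### Section 9.3.3 counts A&E visits and hospital admissions as asthma exacerbations without naming a cause, while 9.4 restricts the A&E part to asthma or lower respiratory conditions and does not say which admissions enter

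*Protocol*

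**What the plan says.** Section 9.3.3, under asthma history, lists the covariate "Number of asthma exacerbations in the year prior to the index date". After the oral corticosteroid criterion, the definition continues "or an Accident and Emergency (A&E) visit, or hospital admission". No diagnosis or reason for contact is given. Contacts close in time are merged by a 14-day rule, which does not filter by cause.

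The same list has two further admission rows, and each of them does name its scope: "Number of all-cause hospitalization in the year prior to the index date" and "Number of respiratory disease related hospitalization in the year prior to the index date".

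Section 9.4 describes the linked hospital data. For emergency attendances it says "HES A&E will be used to ascertain A&E attendance for asthma or low respiratory conditions", and adds "which will be used to calculate the number of asthma exacerbation in the year prior to the index date". For admissions it says that "HES APC will be used to assess hospitalization (all-cause, respiratory disease related, or asthma or lower respiratory condition related") in the year before index, and does not tie any of the three categories to the exacerbation count.

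Section 9.7.1 compares every listed characteristic between Spiriva Respimat initiators and each other group by ASD, and treats 10% or more as meaningful.

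**The concern.** One variable has two descriptions. The section that defines it sets no condition on cause; the section on data sources sets one for A&E and leaves admissions open. An analyst who programs from 9.3.3 would score a fracture seen in A&E, or a planned operation, as an asthma exacerbation. An analyst who programs from 9.4 would not score the A&E visit, and would have to guess about the admission. Section 9.8 says the protocol will be strictly followed and that a second analyst will review or repeat the analytic approach. Both analysts could claim to have followed it and still produce different counts.

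The row matters for the study's purpose. The protocol wants to detect channeling, and the UK indication cited in section 7 includes severe exacerbations in the previous year. Section 7 also says the results may guide the choice of propensity-score variables in later studies. If the count partly reflects general morbidity, a difference in age or cardiac disease could be read as a difference in asthma severity.

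**Working it through.** The check is mainly a comparison of the two sections.

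| Component of the count | 9.3.3 | 9.4 |
|---|---|---|
| A&E visit | no cause stated | asthma or lower respiratory conditions, explicitly linked to the count |
| Hospital admission | no cause stated | three categories listed, none linked to the count |

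**A&E.** The two sections conflict directly. 9.4 prints low respiratory for A&E and lower respiratory for admissions; I read these as the same term.

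**Admissions.** Match the three categories in 9.4 to the rows in 9.3.3. All-cause has its own row. Respiratory disease related has its own row. Asthma or lower respiratory has no row, and it names the same conditions as the A&E restriction. Its only evident use is the exacerbation count. That is an inference; the protocol does not say so.

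**Direction.** Under 9.3.3 as written, the qualifying contacts include all those that qualify under the restricted rule, plus any unrelated ones. With the same merging rule, the count can only equal or exceed the restricted count. The excess is larger in a group with more unrelated hospital contacts.

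**Size.** The protocol gives no rates of exacerbations, A&E visits or admissions, so the size cannot be computed. The mechanism can be illustrated with assumed shares. Suppose 40% of both groups truly had at least one exacerbation, and a share u of the remaining 60% had an unrelated A&E visit or admission. The observed proportion is p = 0.40 + 0.60u, and

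ASD = |p1 − p2| / sqrt([p1(1 − p1) + p2(1 − p2)] / 2).

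| u, group 1 | u, group 2 | p1 | p2 | ASD |
|---|---|---|---|---|
| 25% | 12% | 55.0% | 47.2% | 0.078 / 0.4984 = 15.7% |
| 20% | 12% | 52.0% | 47.2% | 0.048 / 0.4994 = 9.6% |
| 15% | 10% | 49.0% | 46.0% | 0.030 / 0.4992 = 6.0% |

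The true difference is zero in each row. Only the widest assumed gap crosses 10%. The illustration uses a yes/no version of what the protocol defines as a number, and it takes 9.3.3 literally for A&E as well. It shows that a spurious difference is possible, not how large it would be here.

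**The case against.** The strongest reply is that the sections should be read together. The variable is named as a count of asthma exacerbations, 9.4 states how its A&E part is obtained, and the otherwise unused admission category points to the same restriction. On that reading the plan is already cause-restricted, and 9.3.3 is shorthand. This stands as the likeliest intention, and it limits the claim: the documents do not establish that unrelated contacts will be counted. It does not remove the defect, because 9.3.3 is the defining section, it names scope in its neighbouring admission rows but not here, and 9.4 never assigns an admission category to the count.

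Stronger conclusions that a reader might draw are not supported:

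- That 9.4 limits both A&E visits and admissions. It expressly limits only A&E.
- That lower respiratory contacts are wrongly included because pneumonia is a separate comorbidity row. Their inclusion is the sponsor's stated choice for A&E, and descriptive rows may overlap.
- That an admission appearing in more than one row is an error. Respiratory admissions are already contained in all-cause admissions, and 9.7.1 compares the rows separately, with no model for the overlap to distort.
- That only an asthma primary diagnosis should qualify. This is a preference and is not needed to resolve the conflict.

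It is also fair to say that exacerbations are one covariate among many. The named outcomes are arrhythmia and cardiac failure, and other asthma markers, such as the RCP three-question score and respiratory admissions, are tabulated as well.

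**Conclusion.** The point holds as an inconsistency in the definition of one covariate. It is more than detail that could be left to an analysis plan, because the stated rule in 9.3.3, followed literally, gives a wrong count and conflicts with 9.4 on A&E. Unrelated contacts would be scored only if 9.3.3 is programmed as written. In that case the count is biased upward, more so in a group with more general morbidity, and the ASD comparison could suggest channeling by asthma severity that is not there.

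The size is unknown: no contact rates are given, and the assumed shares give spurious ASDs from 6.0% to 15.7%, on both sides of the 10% threshold. The statement about which admissions are intended rests on inference. The passages should be reconciled before programming starts.

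**What to change.** In 9.3.3, state that an A&E visit or a hospital admission counts towards an exacerbation only if it was for asthma or a lower respiratory condition, the restriction that 9.4 already gives for A&E. In 9.4, state that the asthma or lower respiratory category of HES APC admissions feeds the count, and use the same condition wording for both data sources. Keep all-cause and respiratory admissions as their own rows. An asthma-only version of the count can be added as a sensitivity row if wanted; it is optional.

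The cost is wording in two sections and one diagnosis filter. Section 9.4 already describes A&E diagnosis as recorded in HES A&E and already plans cause-specific admission categories, so no new data source is needed. The count will be somewhat smaller than under 9.3.3 as written, and some asthma contacts with poor coding will be missed.
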